5.2 Secondary Efficacy Endpoints

The secondary efficacy endpoints are efficacy, local skin response, and patient reported outcomes. These endpoints will be assessed from screening to Day 57 or study completion.

Efficacy:

- Reduction in number of actinic keratoses: defined as the percent change in actinic keratosis count in the target treatment area on Day 57, as compared to the baseline lesion count.
- Partial clearance of lesions: defined as the proportion of patients with a reduction of 75% or more in the number of clinically visible AKs in the target treatment area at Day 57, compared to baseline.
- Complete clearance of lesions: defined as the proportion of patients with complete clearance of actinic keratoses in the target treatment area.

Local skin response:

Local skin response (LSR) as measured by visual assessment by the investigator using a 4 point scale on six responses for a maximum total of 24, according to the LSR scoring scale.

Patient Reported Outcomes:

- Pain as measured by the 0-10 VAS Numeric Pain Distress Scale (0 = no pain, 5 = moderate pain, 10 = unbearable pain).
- Patient quality of life as measured by Skindex-16 survey

5.3 Safety Evaluations

Evaluations include: adverse event reporting, clinical laboratory sampling, and physician evaluation. Adverse event reporting and physician evaluation will occur at every visit, if applicable. Clinical laboratory sampling will occur at Screening, Day 4, Day 29, Day 57, and early termination (if applicable). Physical Examination will occur at Screening, Day 1, Day 29, and early termination (if applicable).

6 SUBJECT SELECTION

6.1 Study Population

Subjects with a solid organ transplant at least one year from the date of transplantation, with a diagnosis of AK, who meet the inclusion and exclusion criteria, will be eligible for participation in this study.

6.2 Inclusion Criteria

1. Adults at least 18 years old.
2. Subject must be a solid organ transplant recipient at least one year from the date of transplantation.
3. Subjects must be in stable health as confirmed by medical history, per investigator judgement.
4. Subjects must be able to read, sign, and understand the informed consent.
5. Subjects have at least 4 and no more than 20 clinically typical (non-hyperkeratotic/hypertrophic), visible actinic keratoses in a treatment area of approximately 100cm² on the face. Treatment areas will include a single cheek (nasofacial sulcus to tragus, malar cheekbone to jawline and avoiding the lower eyelid and mouth); the forehead (hairline to eyebrows, extending laterally to the root of the helix).
6. Subject must be willing to forego any other treatments on the face, including cryotherapy, tanning bed use and excessive sun exposure while in the study.
7. Subject is willing and able to participate in the study and to comply with all study requirements including concomitant medication and other treatment restrictions.
8. If subject is a female of childbearing potential she must have a negative urine pregnancy test result prior to study treatment initiation and must agree to use an approved method of birth control while enrolled in the study.

6.3 Exclusion Criteria

1. Subjects with an unstable medical condition as deemed by the clinical investigator.

2. Subjects with a history of bone marrow or stem cell transplantation.
3. Subjects with non-melanoma skin cancer in the treatment area.
4. Subjects with hyperkeratotic or hypertrophic AKs.
5. Subjects with any dermatologic disease in the treatment area that may be exacerbated by the treatment proposed or that might impair the evaluation of AKs.
6. Women who are pregnant, lactating, or planning to become pregnant during the study period.
7. Subjects who have previously been treated with ingenol mebutate in study area within the past 8 weeks.
8. Subjects who have used any topical prescription medications for actinic keratosis on the study area within 8 weeks prior to study treatment initiation.
9. Subjects who have used any topical prescription medications for other reason on the study area within 4 weeks prior to study treatment initiation.
10. Subjects who are currently participating in another clinical study or have completed another clinical study with an investigational drug or device on the study area within 30 days prior to study treatment initiation.
11. Subjects with known hypersensitivity to Picato gel or any of the inactive ingredients: isopropyl alcohol, hydroxyethyl cellulose, citric acid monohydrate, sodium citrate, or benzyl alcohol.

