2 STUDY RATIONALE

Actinic keratoses (AK) are precursors to cutaneous squamous cell carcinoma (SCC), and are treated to prevent progression to SCC. First-line therapy for AK include cryotherapy and curettage, which target clinically visible lesions but do not address the subclinical lesions in the field of ultraviolet radiation damage. Field therapy includes topical chemotherapy, immunotherapy, and photodynamic therapy. Ingenol mebutate is the active compound found in *Euphorbia peplus* sap, and has been approved for treatment of actinic keratoses in immunocompetent patients. Ingenol mebutate 0.015% is favored over other topical treatments for treatment of actinic keratoses on the face due to the brief treatment course, high clearance rate, and resolution without sequelae.

There are no data on safety of this medication in immunosuppressed solid organ transplant recipients (OTR). OTR have a high incidence of AK and high risk of developing SCC, and require frequent field therapy. In addition, OTR generally have a higher burden of AK and require treatment of a larger surface area than the 25 cm² area labeled for ingenol mebutate 0.015%. We plan to investigate the safety and efficacy of ingenol mebutate 0.015% in OTR, with a treatment area up to 100 cm².

The rationale for an increased dose and surface area for treatment in this study is that OTR typically have an extensive burden of AK, requiring treatment of larger areas such as those described here. The proposed treatment regimen better reflects the 'real world' need for treatment of a larger surface area while evaluating the safety and local site reactions associated with this treatment regimen.

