10.1 Visit 1 (Screening, Day -14 to 1)

1. Review the study with the subject and obtain written informed consent and HIPAA authorization.
2. Assign the subject a unique screening number.
3. Record demographics data.
4. Record medical history, including a history of actinic keratosis, diagnosis date, and prior actinic keratosis treatments.
5. Record concomitant medications.
6. Perform a complete physical examination.

7. Perform an actinic keratosis count.
8. Collect blood for clinical laboratory tests (chemistry and hematology).
9. Collect urine sample and perform urine pregnancy test (if applicable).
10. Continue to Visit 2 procedures (can occur on the same day), or schedule subject for Visit 2/ Day 1.

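### No exclusion sets a look-back for cryotherapy or curettage on the study field, so recently treated lesions can enter the baseline actinic keratosis count

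*Combined protocol and SAP*

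**What the plan says.** Section 6.3 has four time-limited exclusions on earlier treatment:

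- Exclusion 7: "Subjects who have previously been treated with ingenol mebutate in study area within the past 8 weeks".
- Exclusion 8: "Subjects who have used any topical prescription medications for actinic keratosis on the study area within 8 weeks prior to study treatment initiation".
- Exclusion 9: "Subjects who have used any topical prescription medications for other reason on the study area within 4 weeks prior to study treatment initiation".
- Exclusion 10: subjects now in another clinical study, or who have "completed another clinical study with an investigational drug or device on the study area within 30 days prior to study treatment initiation".

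The Synopsis repeats these four. Procedures appear in three other places. Section 2 states: "First-line therapy for AK include cryotherapy and curettage, which target clinically visible lesions"; it lists photodynamic therapy as a form of field therapy, apart from topical chemotherapy. Inclusion 6 in Section 6.2 requires that the subject be "willing to forego any other treatments on the face, including cryotherapy, tanning bed use and excessive sun exposure while in the study". Section 10.1 asks staff at Screening to "Record medical history, including a history of actinic keratosis, diagnosis date, and prior actinic keratosis treatments", and the schedule in Appendix 1 has a matching Screening line for earlier therapies and procedures.

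Section 10 lets Screening and Visit 2 fall on one day. Section 15.4 takes baseline from Day 1 before dosing or from Screening, and compares the clearance results and the composite LSR score with historical controls.

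**The concern.** The plan treats recent topical therapy of the field as a confounder, and it does not accept cryotherapy once the subject is in the study. It sets no limit on cryotherapy or curettage given as routine care just before entry. These procedures act on visible lesions, which are what the efficacy endpoints count.

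Efficacy is the within-subject change in lesion count to Day 57, with no concurrent arm. If a lesion counted at baseline was already resolving after a procedure, its disappearance is credited to the drug, and nothing in the design would reveal it. Section 9.1.5 gives no rule for counting recently treated lesions.

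Erythema, crusting and erosion left by a procedure are also items on the LSR scale in Appendix III. The planned summary is the mean maximum composite score and its trend, and no adjustment for the Day 1 score is described.

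**Working it through.** The plan states no figure for this point, so there is none to reproduce. The check is a comparison of the criteria, followed by illustrations on assumed inputs.

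**1. Look-back before Day 1, by type of earlier treatment on the study area**

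| Earlier treatment | Look-back | Source |
|---|---|---|
| Ingenol mebutate | 8 × 7 = 56 days | Exclusion 7 |
| Topical prescription for actinic keratosis | 56 days | Exclusion 8 |
| Other topical prescription | 4 × 7 = 28 days | Exclusion 9 |
| Investigational drug or device in another study | 30 days | Exclusion 10 |
| Routine cryotherapy or curettage | none | no criterion |
| Routine photodynamic therapy | unclear | Exclusion 8 only if the photosensitiser counts as a topical prescription |

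**2. Guaranteed procedure-free interval.** Inclusion 6 starts when the subject is in the study. If that means consent, it covers the screening period: at most about 14 days, and 0 days when Screening and Day 1 coincide. The guaranteed interval is therefore 0 days.

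**3. Which lesions matter.** A treated lesion that has gone before the baseline count earns no credit. One that is still counted and later resolves does. If the Screening count serves as baseline, a lesion that resolves between Screening and dosing is credited too.

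**4. Illustration for mean reduction.** Assume that the drug clears t = 0.60 of lesions, that r = 0.80 of recently treated lesions resolve regardless, and that a share f of counted baseline lesions was recently treated. Then

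observed reduction = 1 − [(1−f)(1−t) + f(1−t)(1−r)] = 0.60 + 0.32f.

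For f = 0.1, 0.2 and 0.3 this gives 63.2%, 66.4% and 69.6%, which is 3.2, 6.4 and 9.6 points above 60%.

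**5. Illustration for the 75% responder endpoint.** Take the minimum of 4 lesions (Inclusion 5), so that 3 must clear. Assume that the drug clears each lesion independently with probability q. The probability of response is

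- no recently treated lesion: 4q³(1−q) + q⁴
- one lesion already resolving: 3q²(1−q) + q³
- one lesion that survived a procedure and will not clear: q³

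| q | None | One resolving | One resistant |
|---|---|---|---|
| 0.3 | 0.08 | 0.22 | 0.03 |
| 0.5 | 0.31 | 0.50 | 0.13 |
| 0.7 | 0.65 | 0.78 | 0.34 |

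One resolving lesion adds 13 to 19 points; one resistant lesion takes off 6 to 31.

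**6. Cohort of 20.** With q = 0.5 and 4 lesions each, suppose that 5 subjects have one resolving lesion. The expected responder rate moves from 31% to (15 × 0.3125 + 5 × 0.5)/20 = 36%. If those 5 each have one resistant lesion instead, it falls to (15 × 0.3125 + 5 × 0.125)/20 = 27%. A heavier case has 8 lesions each, with 4 already resolving in 5 subjects: the rate moves from 14% to (15 × 0.1445 + 5 × 0.6875)/20 = 28%.

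**The case against.** The case for leaving the criteria alone has real content.

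- **Entry still requires lesions.** A subject treated shortly before Day 1 qualifies only with at least four typical, visible lesions left, and the count is repeated on Day 1 before dosing. This narrows the gap but does not close it, since no interval is guaranteed.
- **The list is not confined to topical prescriptions.** A reader might infer that it is. Exclusion 10 goes further, though only for another clinical study, and photodynamic therapy may fall under Exclusion 8. Only cryotherapy and curettage are plainly uncovered.
- **Recent procedures may be uncommon.** Section 2 says that these patients often need field therapy and contrasts that with cryotherapy and curettage. It does not show how often recent procedures occur.
- **Direction is not established.** A lesion still visible after a procedure may be resolving or resistant. The last column of the responder table shows that resistant lesions would work against the drug.
- **The consequence is limited.** Efficacy is secondary and descriptive in a pilot that is not powered. For scale, 10 responders of 20 has an exact 95% interval of about 27% to 73%, although a wide interval does not excuse a bias. LSR residue could be noticed, because scores and photographs are taken on Day 1 before dosing.
- **A longer look-back has a cost.** One site must recruit 20 subjects, 10 of them lung recipients, in 6 months. The documents also give no ground for assuming that an interval chosen for topical drugs suits procedures.

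All of this limits the size of the point. None of it supplies the missing look-back, or an analysis that uses the history collected at Screening.

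**Conclusion.** The gap stands: routine cryotherapy or curettage of the study field shortly before Day 1 does not by itself exclude a subject who still has four typical visible lesions. This does not fit well with Exclusions 7 and 8 or with Inclusion 6. The affected results are the lesion-clearance endpoints, the LSR scores and their comparison with historical controls. The primary adverse event endpoint is not the subject of this point.

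A reader might infer that the efficacy results will be inflated by 3 to 10 points. The documents do not support that. The 60%, the 80% and the 10% to 30% are all assumptions, as are the values of q, and the true size cannot be computed. A bias in the drug's favour is the more plausible direction, if most treated lesions still visible at baseline go on to resolve, but it is not shown.

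The change should be made because it is cheap and a single-arm design has no other protection. The study does not fail its primary purpose without it.

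**What to change.** 1. In Section 6.3 and the Synopsis, extend Exclusion 8 to lesion- or field-directed procedures on the study area, naming cryotherapy and curettage and stating whether photodynamic therapy is included. The sponsor should set and justify the look-back; the 8 weeks already used for topical actinic keratosis drugs is the natural reference. The cost is one added phrase and some delayed enrolment.
2. Alternatively, or in addition, record the date and site of the last procedure within the prior-treatment history that Section 10.1 and Appendix 1 already require. In the statistical analysis plan promised in Section 15, prespecify a repeat of the clearance and LSR tables without subjects treated inside that look-back. The cost is two fields on the case report form and one further set of descriptive tables; eligibility and care do not change.

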7 CONCURRENT MEDICATIONS

All subjects should be maintained on the same medications throughout the entire study period, as medically feasible, with no introduction of new chronic therapies.

7.1 Allowed Medications and Treatments

Standard therapy for OTR is allowed except for treatments noted in the exclusion criteria described above and as noted in the prohibited medications section below.

If a patient has a (1) local skin response score of 3 or greater in any individual category, and (2) associated symptoms unrelieved by supportive care such as ice packs and nonsteroidal anti-inflammatory drug (NSAID), then 1% topical hydrocortisone cream or ointment is allowed after Day 4 at the discretion of the investigator.

7.2 Prohibited Medications and Treatments

The following medications are prohibited during the study and administration will be considered a protocol violation: any topical prescription medication on the treatment area during the study.

8 STUDY TREATMENTS

8.1 Method of Assigning Subjects to Treatment Groups

All eligible subjects that have enrolled in the study will be supplied with open-label ingenol mebutate 0.015% gel. The investigator or study staff will record the kit number dispensed to each subject.

8.2 Blinding

Not applicable. This is an open-label study.

8.2.1 Formulation of Test Product

Not applicable.

8.2.2 Formulation of Control Product

Not applicable.

8.2.3 Packaging and Labeling

Ingenol mebutate 0.015% gel is supplied in cartons containing 4 single use tubes.

Each carton (kit) of ingenol mebutate 0.015% will be labeled with the required FDA warning statement, the protocol number, the name of the investigator, patient number, and directions for patient use and storage. Each tube will be labeled with the expiration date.

8.3 Supply of Study Drug at the Site

Leo Pharma will ship ingenol mebutate 0.015% gel to the investigational site. The initial ingenol mebutate 0.015% shipment will be shipped after site activation (i.e., all required regulatory documentation has been received by Leo Pharma and a contract has been executed). Subsequent ingenol mebutate 0.015% gel shipments will be made after site request for resupply.

8.3.1 Dosage/Dosage Regimen

Ingenol mebutate 0.015% gel will be applied topically once a day, for three continuous days. Ingenol mebutate 0.015% gel will be applied to the subject's forehead, left cheek, OR right cheek. Each kit contains 4 tubes of ingenol mebutate 0.015% gel, and subjects will apply 1 kit per day to the investigator-determined site.

Subjects should not apply ingenol mebutate 0.015% gel immediately after taking a shower, or less than 2 hours before bedtime. Subjects MUST AVOID eyes, lips, and mouth while applying ingenol mebutate 0.015% gel.

8.3.2 Dispensing

The investigator or other training study staff will dispense ingenol mebutate 0.015% gel to subjects. Subjects will also be given application instructions (Appendix III).

8.3.3 Administration Instructions

Ingenol mebutate 0.015% gel will be applied topically once a day, for three continuous days. Each kit contains 4 tubes of ingenol mebutate 0.015% gel, and subjects will apply 1 kit per day. Subjects should not apply ingenol mebutate 0.015% gel immediately after taking a shower, or less than 2 hours before bedtime. Subjects should use a new tube for each application.

Ingenol mebutate 0.015% gel will be applied to the subject's forehead, left cheek, OR right cheek. Subjects should visualize each application site (forehead, left cheek, or right cheek) as divided into 4 quadrants. Each kit contains 4 tubes; 1 tube is to be applied to each quadrant. The investigator will specify the application site and instructions during Screening.

A detailed subject hand-out containing the following application instructions will also be provided at Baseline:

1. Open a new tube of ingenol mebutate 0.015% gel.
2. Squeeze gel from the tube onto a fingertip.
3. Apply gel onto the center of Quadrant 1, spreading the gel evenly over the entire skin quadrant.
4. Check off Quadrant 1 on instruction sheet after gel is applied.
5. Open a 2nd tube of ingenol mebutate 0.015% gel.
6. Squeeze gel from the tube onto a fingertip.
7. Apply gel onto the center of Quadrant 2, spreading the gel evenly over the entire skin quadrant.
8. Check off Quadrant 2 on instruction sheet after gel is applied.
9. Open a 3rd tube of ingenol mebutate 0.015% gel.
10. Squeeze gel from the tube onto a fingertip.
11. Apply gel onto the center of Quadrant 3, spreading the gel evenly over the entire skin quadrant.
12. Check off Quadrant 3 on instruction sheet after gel is applied.
13. Open a 4th tube of ingenol mebutate 0.015% gel.
14. Squeeze gel from the tube onto a fingertip.
15. Apply gel onto the center of Quadrant 4, spreading the gel evenly over the entire skin quadrant.
16. Check off Quadrant 4 on instruction sheet after gel is applied.
17. Allow the treated area to dry for 15 minutes.
18. Wash hands right away after applying ingenol mebutate 0.015% gel.
19. After use, place tubes into the bag provided, and return to study site at the next visit.

Subjects are not responsible for medication re-supply, as they will be provided with enough tubes at Baseline. Subjects MUST AVOID eyes, lips, and mouth while applying ingenol mebutate 0.015% gel.

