10.2 Visit 2 (Day 1)

1. Record any Adverse Events.
2. Concomitant medications review.
3. Perform a complete physical examination.
4. Perform an actinic keratosis count.
5. Perform a local skin response assessment.
6. Subject to perform a VAS pain assessment.
7. Subject to complete the Skindex-16.
8. Perform photography in treatment area.
9. Collect urine sample and perform urine pregnancy test (if applicable).
10. Dispense a kit of ingenol mebutate 0.015% gel; subject will complete the first application under the investigator's supervision in the clinic.
11. Dispense subject 2 additional kits for use on Day 2 and Day 3. Subject will also be provided with a detailed application instructions hand-out.
12. Schedule subject for Visit 3/ Day 4.

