APPENDIX II. SUBJECT INSTRUCTIONS FOR USE

Instructions for Use
Ingenol Mebutate gel, 0.015%

Be sure that you read, understand, and follow these Instructions for Use before you use ingenol mebutate gel, 0.015% for the first time.

Treatment Diary

Day 1: Did you apply all 4 tubes to the treatment area?

Quadrant 1 Quadrant 2 Quadrant 3 Quadrant 4

No, please specify reason: _____

Day 2: Did you apply all 4 tubes to the treatment area?

Quadrant 1 Quadrant 2 Quadrant 3 Quadrant 4

No, please specify reason: _____

Day 3: Did you apply all 4 tubes to the treatment area?

Quadrant 1 Quadrant 2 Quadrant 3 Quadrant 4

No, please specify reason: _____

IMPORTANT:

- **Always use ingenol mebutate gel exactly as your study doctor tells you.** Check with your study doctor if you are not sure.
- Only use ingenol mebutate gel to treat actinic keratosis on your assigned study treatment area.

- **Assigned study treatment area:** _____
- Apply ingenol mebutate gel to the skin area to be treated 1 time each day for 3 days in a row. Day 1 will be applied at your study visit, days 2 and 3 will be applied at home.
- Wash your hands well with soap and water after applying it. After applying ingenol mebutate gel, be careful to keep ingenol mebutate gel on treated area from coming into

contact with your eyes. Irritation may happen if you get ingenol mebutate gel in your eyes.

- Use a new kit (4 tubes) for each day of treatment. Avoid touching the treatment area or doing activities that cause a lot of sweating for 6 hours after applying ingenol mebutate gel. After 6 hours you may wash the treatment area with a mild soap and water.

DO NOT:

- apply right after taking a shower or less than 2 hours before bedtime.
- **get ingenol mebutate gel in, around, or near your eyes. Do not touch your eyes while you are applying ingenol mebutate gel (if you accidentally get ingenol mebutate gel in your eyes, flush them with large amounts of water and get medical care as soon as possible).**
- **get ingenol mebutate gel in, around, or near your lips and mouth.**

Applying Ingenol Mebutate gel

Step 1. Open a new kit (containing 4 tubes) each time you use ingenol mebutate gel.

Step 2. Select the first tube. Remove cap from tube just before use. (See Figure A).

[figure not shown]

Figure A

Step 3. Squeeze the gel from the tube onto a fingertip. (See Figure B).

[figure not shown]

Figure B

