Step 4. Visually divide your (treatment area – cheek or forehead) into 4 quadrants. (See Figure C).

[figure not shown]

Figure C

Step 5. Apply gel onto the center of Quadrant 1, spreading the gel evenly over the entire skin quadrant.

Step 6: Select the second tube.

Step 7: Remove cap from the tube, and squeeze the gel from the tube onto a fingertip.

Step 8: Apply gel onto the center of Quadrant 2, spreading the gel evenly over the entire skin quadrant.

Step 9: Select the third tube.

Step 10: Remove cap from the tube, and squeeze the gel from the tube onto a fingertip.

Step 11: Apply gel onto the center of Quadrant 3, spreading the gel evenly over the entire skin quadrant.

Step 12: Select the fourth tube.

Step 13: Remove cap from the tube, and squeeze the gel from the tube onto a fingertip.

Step 14: Apply gel onto the center of Quadrant 4, spreading the gel evenly over the entire skin quadrant.

Step 15: DO NOT get in, around or near your eyes, lips, and mouth. Allow the gel to dry for 15 minutes.

Step 16: Wash your hands right away after applying the gel. (See Figure D).

[figure not shown]

Figure D

Step 17: After use, place tubes into the bag provided, and return to study site at your next visit.

Repeat the above steps for each day of treatment.

How should I store the Ingenol Mebutate gel?

[figure not shown]
- Store the gel in a refrigerator at 36°F to 46°F (2°C to 8°C). Do not freeze.
- The gel has an expiration date (exp) marked on the end of the tube. Do not use the gel after this date.
- After use, place tubes into the bag provided, and return to study site at your next visit.

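### Application instructions number the 15-minute drying wait before hand washing, although the washing step calls for immediate washing

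*Combined protocol and SAP*

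**What the plan says.** Section 8.3.3 lists 19 steps for each day's application. After the fourth quadrant is treated and checked off (step 16), step 17 reads "Allow the treated area to dry for 15 minutes" and step 18 reads "Wash hands right away after applying ingenol mebutate 0.015% gel".

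Appendix II, the sheet the patient takes home, keeps that order. Step 14 is the fourth quadrant. Step 15 opens with a warning to keep the gel away from the eyes, lips and mouth, then says "Allow the gel to dry for 15 minutes". Step 16 says "Wash your hands right away after applying the gel".

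Ahead of its numbered steps, Appendix II has general cautions. Under the heading IMPORTANT it says "Wash your hands well with soap and water after applying it" and warns that gel in the eyes may irritate. Its list of prohibitions includes "Do not touch your eyes while you are applying ingenol mebutate gel".

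On setting, Section 10.2 says that the "subject will complete the first application under the investigator's supervision in the clinic", and Appendix II says that "days 2 and 3 will be applied at home".

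**The concern.** A numbered patient sheet is meant to be worked through in order. Someone who completes each step before starting the next would finish the fourth quadrant, wait 15 minutes, and only then wash. Someone who goes by the words of the washing step would wash at once. The same instruction therefore supports two different times.

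Washing is the step that takes the gel off the fingers. Each tube is squeezed onto a fingertip and spread by hand, four times per application, on the cheek or forehead. Under Section 6.2 the forehead area runs down to the eyebrows. The sheet itself treats eye contact as a hazard and tells patients to flush the eye and seek care if it happens. A step that guards against that hazard should have only one reading.

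What is at stake is small and practical: avoidable time with an irritant gel on the fingers close to the eyes. It does not touch the endpoints, sample size or analysis.

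**Working it through.** The plan gives no figure to reproduce. The check is a comparison of texts and a count of how often the sheet is used without supervision.

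**Order and wording in the two lists**

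| | Section 8.3.3 | Appendix II |
|---|---|---|
| Fourth quadrant finished | steps 15–16 (applied, then checked off) | Step 14 |
| 15-minute drying | step 17 | Step 15 |
| Hand washing | step 18 | Step 16 |
| Timing given by the washing step | immediately after application | immediately after application |

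The conflict is the same in both places. Counting from the end of the fourth quadrant:

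- by the wording of the washing step, the delay is 0 minutes;
- by the step numbers, the delay is 15 minutes.

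**Whether other text settles the order**

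- The general washing line in Appendix II ("Wash your hands well with soap and water after applying it") ties washing to application and mentions no wait. That favours the immediate reading, but washing after the drying period is also after application.
- The instruction "Do not touch your eyes while you are applying ingenol mebutate gel" is limited to the time of applying and does not extend to the drying period.
- The caution for the period after application concerns gel on the treated skin, not gel on the fingers.
- The warning that opens Appendix II Step 15, and the general prohibition on getting gel near the eyes, do apply during drying. They state what to avoid; they do not say when to wash.

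None of these fixes the order of washing and drying.

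**Use of the sheet without supervision**

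Inputs: 20 patients (synopsis; Section 4.1); 3 daily applications (Section 8.3.1); Day 1 supervised (Section 10.2); Days 2 and 3 at home (Appendix II).

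- Planned applications: 20 × 3 = 60.
- Supervised on Day 1: 20 × 1 = 20.
- At home: 60 − 20 = 40.

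The 40 assumes that all 20 patients enrol and complete dosing, so it is an upper bound on home uses of the sheet. It does not count misreadings. The Appendix II diary asks only which quadrants were treated and, if any were missed, why, so it would not show the site whether washing was delayed.

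**The case against.** The best answer is that the words already give the right instruction. The washing step takes its timing from application, not from drying. Drying is passive and concerns the treated skin, so it can run while the hands are washed, and the two steps are compatible. The general washing line comes before the numbered steps and says nothing about waiting. The eye is also protected elsewhere: Step 15 of Appendix II, the drying step itself, opens with a warning about the eyes, and the list of prohibitions has a general one with no time limit. Finally, each patient goes through the sequence with staff on Day 1 before using the sheet alone. On this view, the point is a copy-edit.

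Much of this stands. Immediate washing is the evident intent, eye protection does not rest on the step order alone, and the supervised first application may well resolve the doubt for many patients. The figure of 40 says nothing about error.

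What it does not do is remove the second reading. The sheet does not say that washing may run alongside drying, and the protocol does not say that staff address the order on Day 1. At home, the written list is the guide. If the intent is clear, the numbering should match it.

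**Conclusion.** The point holds as a minor ambiguity in a safety instruction. In both lists the step order and the wording of the washing step give different times, 15 minutes against 0, and no other text decides between them. It is not an instruction to delay washing, and it should not be described as one.

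The reach is at most 40 unsupervised applications, on the assumption of full enrolment and completed dosing. The share that would be misread is unknown. Any effect on eye events, or on the proportion of patients with any adverse event, cannot be quantified from the documents, and none is claimed. A correction is desirable but nothing in the analysis depends on it.

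**What to change.** Move hand washing ahead of drying in both lists, and name soap and water in the step itself:

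- **Section 8.3.3:** exchange steps 17 and 18, so that washing comes directly after the fourth quadrant is checked off at step 16 and the drying wait follows.
- **Appendix II:** exchange Steps 15 and 16, so that washing comes directly after Step 14. The reference to Figure D moves with the washing step; the eye, lip and mouth warning stays with the drying step.

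Suitable wording for the pair: *Wash your hands immediately with soap and water. Then leave the treated area to dry for 15 minutes.*

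The cost is one moved line in each of two lists and IRB review of the revised patient sheet. No endpoint, sample size or analysis changes.
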